A prospective randomized single blind controlled study on maintenance therapy with Sintilimab after radiotherapy and chemotherapy for locally advanced head and neck tumors based on peripheral blood CD8TEX detection

Main researcher: [name]

Plan version number: 1.0 version

Date of formulation: January 25, 2024

Main research unit: Second Affiliated Hospital of Zhejiang University

1. Introduction to research background:

Head and neck squamous cell carcinoma (HNSCC) includes cancers of the mouth, oropharynx, larynx and hypopharynx. The incidence rate ranks the sixth with a mortality rate of 40-50%. It is a serious disability and life-threatening disease. Due to the unique anatomical location, the surgical disability rate of HNSCC is high, which seriously affects the quality of life of patients. Radiation therapy is a very important local treatment for malignant tumors. Radiation therapy not only protects organ function and has cosmetic effects, but also has a long-term survival comparable to surgical treatment for early HNSCC patients receiving radiation therapy. However, over 60% of HNSCC patients are initially diagnosed as locally advanced. For patients with locally advanced stage who cannot undergo surgery, the current standard treatment regimen is synchronous radiotherapy and chemotherapy (CRT) or synchronous targeted treatment with cetuximab, followed by clinical follow-up. However, there are still relatively high rates of local recurrence or distant metastasis in patients with locally advanced head and neck tumors after radiotherapy and chemotherapy. The 3-year PFS rate is about 60%, 50% of relapses occur within 2 years after radiotherapy and chemotherapy, 20% to 30% of patients experience distant metastasis, and the overall 5-year survival rate is less than 50%. Therefore, it is necessary to further optimize the maintenance treatment plan after radiotherapy and chemotherapy, in order to improve the clinical cure rate of patients with locally advanced head and neck tumors.

Immunotherapy has achieved significant breakthroughs in recurrent and metastatic head and neck tumors. Studies on various tumor models have shown that tumor infiltration of PD-1+CD8+depleted T cells (CD8+TEX) is an important mechanism for the reduction of anti-tumor function and tumor progression in the body. Immunotherapy can reactivate T cell responses by blocking the PD-1 pathway. A

clinical study by Checkmate 141 showed that anti PD-1 monoclonal antibodies showed long-lasting efficacy in treating recurrent and metastatic HNSCC, with a nearly three fold increase in OS rate at 2 years (16.9% vs 6.0%). Therefore, in 2016, the first anti PD-1 antibody was approved by the FDA for recurrent or metastatic HNSCC that failed platinum chemotherapy. Radiation therapy can directly kill tumor cells while also reshaping the local immune microenvironment of the tumor, including the release of pro-inflammatory molecules and infiltration of immune cells. The subgroup analysis of KEYNOTE-001 and PEMBRO-RT studies found that patients who had previously undergone radiotherapy had better immunotherapy efficacy after recurrence and metastasis. However, studies on immunotherapy in locally advanced HNSCC have all failed, including the JAVELIN HEAD AND NECK 100 study comparing the efficacy of Avelumab combined with CRT treatment and Avelumab maintenance therapy with CRT standard treatment, and the GORTEC REACH study comparing the efficacy of Avelumab combined with cetuximab combined with radiotherapy and Avelumab maintenance therapy with standard treatment. Both studies used immunosynchronous therapy at the beginning of radiotherapy without adaptive screening, and the PFS of both studies showed a trend of numerical benefits but no statistical significance. Therefore, can better biomarkers be selected to screen suitable HNSCC patients for maintenance therapy after synchronous radiotherapy and chemotherapy?

At present, there are no research reports on the changes of CD8+TEX cells in the tumor immune microenvironment after radiotherapy. In our preliminary research, we found in the HNSCC mouse tumor model that the proportion and quantity of PD-1+CD8+TEX cells in the tumor and peripheral blood significantly increased with the prolongation of time after radiotherapy, and the combination of immunotherapy at the end of radiotherapy or 7 days after radiotherapy had the best therapeutic effect. We further tested the proportion of TEX in human peripheral blood and the expression level of PD1 during and after synchronous radiotherapy and chemotherapy, and found a similar trend as in the mouse model. So we speculate whether the proportion of peripheral blood CD8+TEX cells and the expression level of PD1 can be used as a suitable screening for immunotherapy. In the early stage, we retrospectively analyzed three patients who underwent immune maintenance therapy after synchronous radiotherapy and chemotherapy, and found that they have been followed up for three years, and no PFS time has been obtained. This study aims to ensure that patients receive standard treatment. By screening the proportion of CD8+TEX cells in peripheral blood and the expression level of PD1, patients with upregulation of CD8TEX in peripheral blood after radiotherapy or patients with PD1 expression levels higher than normal were randomly divided into two groups: one group received maintenance therapy for immunity, and the other group received placebo comparison to evaluate PFS time.

2. Research Purpose

2.1 Research Purpose:

A prospective randomized single blind controlled study on maintenance therapy with Sintilimab after radiotherapy and chemotherapy for locally advanced head and neck tumors

2.2 Main study endpoints:

Evaluation of progression free survival (PFS) and 1-year progression free survival (PFS) in two groups of patients with locally advanced head and neck tumors after radiotherapy and chemotherapy (using RECIST 1.1 criteria)

2.3 Secondary study endpoints:

Evaluation of overall survival (OS), safety and tolerability, changes in quality of life relative to baseline, and time to deterioration in maintenance therapy with Xindilimab in patients with locally advanced head and neck tumors after radiotherapy and chemotherapy (EORTC QLQ-C30 and H&N-35)

The primary safety analysis will be conducted based on subjects who experience toxicity (as defined by CTCAE standards). CTCAE version 5.0 will be used to evaluate safety through reported adverse events. The relationship between adverse events and drugs, onset time, duration of events, their resolution, and any concomitant medication will be recorded. Adverse events (AEs) will be analyzed, including but not limited to all AEs, SAEs, lethal AEs, and laboratory changes.

2.4 Exploratory study endpoint:

Explore biomarkers for predicting efficacy and adverse reactions, and obtain better guidance on the combination therapy and safety of immunotumor drugs. In order to identify novel biomarkers, we collected biological samples: 10-20ml of blood (before treatment and during efficacy evaluation) to support the analysis of cellular components (such as DNA, proteins, etc.), such as whole exome gene testing, TMB, PD-L1, MRD, etc.

3. Research design and methods:

3.1 Inclusion criteria:

- (1) Male or female, age ≥ 18 years old, ≤ 75 years old.
- (2) Localized advanced head and neck tumors with T3 or N+ or above that have been histologically confirmed as inoperable.
- (3) Patients undergoing synchronous radiotherapy and chemotherapy
- (4) ECOG physical fitness status ranges from 0 to 1 point.
- (5) The expected lifespan is at least 12 weeks.
- (6) At least one measurable lesion
- (7) Hematology examination absolute neutrophil count (ANC) $>1.5 \times 10^9/L$, hemoglobin $>8g/dL$ and platelets $>100 \times 10^9/L$ (based on the normal value of the clinical trial center).
- (8) Prothrombin time (PT) <1.5 times the upper limit of normal value and normal thromboplastin time (APTT) <1.5 times the upper limit of normal value.
- (9) Laboratory tests show that serum creatinine is less than or equal to 1.5 times the upper limit of the normal reference range (if serum creatinine increases, 24-hour urine must be collected, except for those with a 24-hour creatinine clearance rate $>50ml/min$).

- (10) When there is no liver metastasis, ALT or AST is less than or equal to 2.5 times the upper limit of the normal reference range, and serum total bilirubin is less than or equal to 1.5 times the upper limit of the normal reference range; For patients with liver metastasis, ALT or AST is less than or equal to 5 times the upper limit of the normal reference range, and serum total bilirubin is less than or equal to 3 times the upper limit of the normal reference range.
- (11) Women of childbearing age must be willing to use adequate contraceptive measures during the study drug treatment period.
- (12) Signed informed consent form.
- (13) At the end of radiotherapy, the proportion of peripheral blood PD1+CD8T cells is greater than 10%, or more than twice the baseline

3.2 Exclusion criteria:

- (1) Active autoimmune diseases that require systemic treatment (i.e. the use of disease relieving drugs, corticosteroids, or immunosuppressants) have occurred within the past 2 years. Alternative therapies (such as thyroid hormone, insulin, or physiological corticosteroid replacement therapy for adrenal or pituitary insufficiency) are not considered systemic treatments.
- (2) Diagnosed as immunodeficiency or undergoing systemic steroid therapy or any other form of immunosuppressive therapy within 7 days prior to the first administration of the trial treatment. After consulting with the sponsor, the use of physiological doses of corticosteroids may be approved.
- (3) It is known that there are other malignant tumors that are progressing or require active treatment. Excluding skin basal cell carcinoma, skin squamous cell carcinoma, or cervical carcinoma in situ that have already undergone curative treatment.
- (4) Active infections that require systemic treatment.
- (5) There is a possibility of confusing the trial results, obstructing the participant's full participation in the study due to medical history or evidence of illness, abnormal treatment or laboratory values, or the researcher believing that participating in the study is not in the best interest of the participant.
- (6) It is known that there are mental or substance abuse disorders that may affect compliance with the trial requirements.
- (7) Female subjects who are pregnant or breastfeeding, or expected to conceive during the planned trial period or 180 days after the last dose of study treatment, or male subjects whose spouses are preparing to conceive.
- (8) Known history of human immunodeficiency virus (HIV) (HIV 1/2 antibody) infection.

3.3 Research Design:

This study is a prospective single blind randomized controlled clinical trial of maintenance therapy with Xindilimab based on peripheral CD8TEX screening after standard radiotherapy and chemotherapy for locally advanced head and neck tumors. Synchronous radiotherapy and chemotherapy are routine standard treatments and do not require the use of immunotherapy drugs in this study. Blood samples were collected before and after radiotherapy, and participants were screened and evaluated according to the inclusion and exclusion criteria of the protocol within 28 days before randomization. Patients who

agree to participate in this study will sign an informed consent form (ICF) prior to the screening process. After completing all screening activities, eligible participants can start receiving study treatment. According to the estimated sample size, a total of 104 patients are planned to be enrolled and randomly assigned equally to the experimental group and control group. The treatment cycle for the study is 21 days. The experimental group starts treatment within one month after the end of radiotherapy and chemotherapy. On the first day of each cycle, intravenous treatment with Sintilimab is given, with a cycle of 21 days. It is expected to be administered for a total of 18 cycles, or until the disease progresses; The control group received placebo treatment. The experimental group underwent routine blood tests, liver and kidney function, myocardial enzyme spectrum, thyroid function, electrocardiogram every 2 cycles, and CT scans every 4 cycles to evaluate toxic side effects; The control group underwent the same frequency of follow-up and observation. The study started on January 1, 2024 and ended on January 1, 2027, to explore the efficacy of maintenance therapy with Xindilimab after radiotherapy and chemotherapy for locally advanced head and neck tumors.

Research plan:

Intravenous infusion of Sintilimab, D1, once every 3 weeks

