3.4.3 Efficacy evaluation

Inspection items	Inspection time and related instructions
Imaging examination	Complete baseline assessment within 1 month before treatment, and treat every 3 months Chest and abdominal CT examination evaluation

3.4.4 Testing items and time after discontinuation/withdrawal from the study (once every 9 weeks since the last medication use)

Inspection items	Inspection time and related instructions
Telephone follow-up	Telephone follow-up every two months

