The medical records, imaging data, drug use registration form, subject code table, serious adverse event report form and other data of the subjects are kept confidential, and these materials are not disclosed to the public outside the scope permitted by relevant laws and/or regulations. The drug regulatory department, the sponsor, and their authorized supervisory personnel, as well as the ethics committee, have the right to access relevant trial data and original records with the consent of the main researchers involved in the trial.

4. Informed consent

Before participants participate in the study, the researcher is responsible for fully explaining the research purpose, methods, expected benefits, and potential hazards to the participants, in order to further obtain voluntary written consent from the participants or their guardians (if permitted by local regulations). The legal representative refers to an individual or institution who, in accordance with legal requirements and with the authorization of the subject or the law, can make consent on behalf of the subject to participate in clinical research. ICF should be written in the native language of the potential subject population.

Researchers should comply with relevant regulatory requirements, GCP, and ethical principles derived from the Helsinki Declaration to obtain written consent from participants. Before providing ICF and its revised versions to potential subjects, approval from IEC/IRB should be obtained. Researchers should ensure that each participant is informed that they can voluntarily terminate the study at any time, and that each participant has the opportunity to ask questions and have time to reflect on the information obtained.

The ICF should be obtained before the participants participate in the study and the consent form should be kept in the research center as a document. The ICF should be signed by the subject themselves or their legal representative (if permitted by local regulations), as well as the researcher's name and date. The original signed ICF should be kept at the research center and a copy of the signed consent form should be provided to the subject or their legal representative. The date of obtaining informed consent should be recorded in the medical records and original records.

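### Inclusion (11) ends the contraception commitment with treatment, 160 to 180 days before the protocol's own post-dose conception window closes

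*Protocol*

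**What the plan says.** Two entry criteria in the Protocol bear on pregnancy in female participants.

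- Section 3.1, inclusion (11): "Women of childbearing age must be willing to use adequate contraceptive measures during the study drug treatment period". No period after the last dose is added.
- Section 3.2, exclusion (7): women who are pregnant or breastfeeding are excluded, and so are those "expected to conceive during the planned trial period or 180 days after the last dose of study treatment".

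Section 3.3 gives the dosing schedule: "On the first day of each cycle, intravenous treatment with Sintilimab is given, with a cycle of 21 days", and "It is expected to be administered for a total of 18 cycles, or until the disease progresses".

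After discontinuation, the only item listed in section 3.4.4 is "Telephone follow-up every two months", with no contraception or pregnancy content. The tests listed before dosing in section 3.4.2 include no pregnancy test.

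**The concern.** By writing 180 days after the last dose into exclusion (7), the protocol itself marks that period as one in which conception should not occur. Exclusion (7), however, is judged once, at screening, and asks only what the woman expects. It places no duty on her afterwards. The one contraception commitment in the visible text is inclusion (11), and that stops with treatment.

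Planned pregnancy after treatment is therefore screened out. Unplanned pregnancy, or a change of mind, is not covered. What is at stake is possible fetal exposure in the months after the last infusion. No trial result depends on it.

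**Working it through.** **Inputs**

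- Post-dose window: 180 days from the last dose (section 3.2, exclusion (7)). The protocol states this figure and does not derive it, so there is nothing to reproduce. It is used here as the protocol's own benchmark.
- Cycle length 21 days, dosing on day 1, 18 cycles planned or until progression (section 3.3).
- End of the study drug treatment period: not defined. Two readings are taken: it ends at the last dose, or on day 21 of the last cycle, which is 20 days after a day-1 dose.

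**Do the two criteria together close the window?** Take a woman of childbearing age who does not expect to conceive and who will use contraception only while treated.

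- Inclusion (11): met, because she is willing for the treatment period.
- Exclusion (7): not triggered, because she has no expectation of conceiving.

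She can be enrolled, and no visible text asks for contraception once treatment ends.

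**Day count for a full course**

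- Last dose: 1 + (18 − 1) × 21 = day 358.
- End of cycle 18: 18 × 21 = day 378.
- End of the 180-day window: 358 + 180 = day 538.
- Uncovered time if the period ends at the last dose: 538 − 358 = 180 days.
- Uncovered time if it ends on day 21 of the last cycle: 538 − 378 = 160 days. Counting a full 21 days after the dose gives 180 − 21 = 159 days, an immaterial difference.

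**Early stopping.** If the last dose falls on any day d, the window closes on d + 180 and the treatment period ends on d or d + 20. The gap is again 180 or 160 days, whatever d is.

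**Generous readings.** Suppose the treatment period were stretched to the 9-week point after the last dose named in the heading of section 3.4.4. The gap would still be 180 − 63 = 117 days. Stretched to the 12-week maximum suspension in section 3.5, it would be 180 − 84 = 96 days. No reading tried here closes it.

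**The case against.** The strongest reply is that the instruction governing a participant's behaviour after her last dose normally sits in the consent form, and those pages are not available. The content of section 3.4.1 (baseline evaluation) is not visible either, and the adverse-event section breaks off at a figure that is not shown. A 180-day instruction may exist there. This stands as a limit: it cannot be said that participants lack such an instruction. It does not remove the point, because inclusion (11) is visible, states a duration, and states one shorter than the protocol's own window. If the consent form does say 180 days, the criterion still needs to be brought into line with it.

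A second reply is that the criteria address different things, willingness to use contraception and expectation of conceiving, and need not share a time frame. It is true that they are compatible, and that no visible text says outright that contraception is needed for 180 days; that step is an inference from exclusion (7). The inference is short, since the protocol offers no other reason for looking 180 days past the last dose.

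A third reply is that an investigator could use exclusion (5), or a broad reading of exclusion (7), to keep out a woman who intends no contraception after treatment. That discretion exists, but neither criterion requires contraception after treatment.

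Finally, few participants may be affected, and those on placebo have no sintilimab exposure. Both observations bear on the size of the risk. They do not argue for different wording, because under single blinding one rule would apply to both arms.

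**Conclusion.** The concern holds as a minor drafting gap in participant safety. In the criteria shown, the contraception commitment ends 160 to 180 days before the protocol's own window closes, and unplanned pregnancy in that interval is not addressed. The range rests on two assumptions: that the 180 days in exclusion (7) is the right benchmark for contraception, and that the undefined treatment period ends somewhere between the last dose and day 21 of the last cycle.

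The gap applies to women of childbearing age among the 104 planned patients; their number is not given. Whether the consent form already covers the interval cannot be determined from the document. Sample size, endpoints and efficacy analysis are unaffected.

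**What to change.** Amend inclusion (11) so that the required willingness to use contraception covers the study drug treatment period and the 180 days after the last dose, matching exclusion (7). Because both ends are then counted from the last dose, the gap falls to 0 days under either reading of the treatment period. Check that the consent form gives the same 180 days, since that is where participants would read the instruction.

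The cost is a minor amendment of one phrase. If the consent form also has to change, section 4 applies: "Before providing ICF and its revised versions to potential subjects, approval from IEC/IRB should be obtained". The efficacy analysis needs no change.

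### The protocol is single blind without saying who is blinded, and it provides no masked assessment of the RECIST progression that decides the primary endpoint

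*Protocol*

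**What the plan says.** The title, section 2.1 and section 3.3 of the protocol all describe a single-blind trial. In 3.3: "This study is a prospective single blind randomized controlled clinical trial of maintenance therapy with Xindilimab". The same section gives controls a placebo ("The control group received placebo treatment") and matches their visits to the experimental arm ("The control group underwent the same frequency of follow-up and observation"). Section 1 says what the placebo is for: "the other group received placebo comparison to evaluate PFS time".

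Section 2.2 sets the primary endpoints: "Evaluation of progression free survival (PFS) and 1-year progression free survival (PFS) in two groups of patients", assessed "using RECIST 1.1 criteria". Section 3.3 plans up to 18 cycles of treatment, ending earlier if the disease progresses.

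Imaging appears in two places. Section 3.4.3 lists, every 3 months, "Chest and abdominal CT examination evaluation". Section 3.3 has "CT scans every 4 cycles to evaluate toxic side effects". Neither names a reader, says who assigns the RECIST category and date, or says whether that person knows the arm. Nothing in the available text describes masked, independent or central review, or an unblinding procedure.

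**The concern.** Every PFS event other than a death is a judgement. Someone decides whether a lesion has grown enough, whether a new finding counts, and whether to call progression now or wait for the next scan. Here the same call stops study treatment. An assessor who knows that a patient is on sintilimab, and hopes for benefit, has a reason to wait for one more scan. The same reason does not apply to a patient known to be on placebo. Later calling in one arm moves PFS and 1-year PFS in the same direction, towards the tested drug.

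The usual obstacle to masking is the absence of a placebo, and that obstacle is missing here. Placebo and same-frequency follow-up are already planned in both arms. As written, though, the plan does not say that this protection reaches the person who calls progression.

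**Working it through.** The plan gives no figure for assessor bias, so there is none to reproduce. Its sample size of 104 cannot help: section 3.3 states it without alpha, power, effect or dropout. The check has two parts.

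**1. What the text establishes**

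- Single blind: stated three times.
- Who is blinded: not stated.
- Who reads the scans and calls progression: not stated.
- Masked assessment: not provided.
- Indirect evidence: the suspension and discontinuation rules in 3.5 are written for sintilimab alone, and suspensions beyond 12 weeks are discussed with the sponsor, with no placebo counterpart and no unblinding step. That fits treating staff who know the arm, but it is an inference.

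**2. Illustration of size**

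From the protocol:
- 104 patients allocated equally, so 52 per arm (3.3)
- 3-year PFS of about 60% (section 1)
- CT every 4 cycles of 21 days, so every 12 weeks (3.3)
- study period of 3 years (3.3)

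Assumed:
- no true effect
- exponential event times
- uniform accrual over 1.5 years
- control arm read without bias
- every event deferrable
- the deferral shares themselves

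*Hazard and events.* The hazard is −ln(0.60)/3 = 0.1703 per year, so 1-year PFS is exp(−0.1703) = 84.3%. The expected event share at the 3-year cut is 1 − [exp(−0.1703 × 1.5) − exp(−0.1703 × 3)]/(0.1703 × 1.5) = 1 − (0.7746 − 0.6000)/0.2554 = 0.316. This gives 104 × 0.316 = 32.9 events. Detection only at scans lowers this to about 31.

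*1-year PFS, by hand.* Scans fall at weeks 12, 24, 36 and 48. Deferral by one scan changes 1-year status only for progressions found at week 48, which move to week 60. Their share is exp(−0.1703 × 36/52) − exp(−0.1703 × 48/52) = 0.8888 − 0.8546 = 0.034. Deferring all of them adds 3.4 points; deferring half adds 1.7.

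*Hazard ratio and false positives, by simulation* (2,500 and 3,000 null trials per setting in two separate runs; a value appears once where only one run gave it):

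| Active-arm progressions deferred one scan | Apparent HR | 1-year PFS difference (points) | Significant in favour of sintilimab |
|---|---|---|---|
| none | 1.00 | 0 | 2.3–2.7% |
| 25% | 0.97 | +0.9 | 3.2% |
| 50% | 0.94–0.95 | +1.6 to +1.7 | 3.3–3.6% |
| 100% (extreme bound) | 0.87 | +3.4 to +3.5 | 5.5–6.4% |

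*Cross-check of the last row.* With 31 events and a spurious HR of 0.87, the log-rank statistic shifts by √(31/4) × −ln(0.87) = 2.784 × 0.139 = 0.388. The chance of a favourable result at the nominal 2.5% is 1 − Φ(1.960 − 0.388) = 5.8%, inside the simulated range.

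*Sensitivity to accrual.* Accrual of 0.5 to 2.5 years gives about 39 down to 26 events (exponential times, ignoring scan detection). A spurious HR of 0.9 would then give favourable false positives of 5.1% down to 4.5%, so the assumed accrual length matters little.

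**The case against.** The strongest objection is that the protocol never says the assessor is unmasked. A reader might infer that nobody who reads scans is masked. The documents do not support that: single blind meaning patient-blind is a convention, not a statement in the protocol. The available text also passes from section 4 to section 7, has nothing under 3.4.1 and breaks off within 7.3, so silence is weaker evidence than in a complete document. This stands, and it limits the point to an unspecified blinded party and no provision for masked assessment. The point survives in that form, because masking has to be arranged before scans are read and an analysis plan cannot supply it later.

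A reader might also infer that any bias would be beyond repair. That goes too far. CTs are scheduled in both arms and section 3.8 keeps imaging data with the subject's record, so a masked re-read could recover part of it. It could not recover scans never taken after an early call.

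The illustration depends on behaviour for which the documents give no figure. At 25 to 50% deferral the shift in false positives is small, and simulation error is about 0.3 points. Deaths count in PFS and cannot be deferred, so treating every event as deferrable overstates the effect. This also stands.

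Finally, letting only pharmacy or infusion staff know the arm would in effect make the trial double blind. That would need a matching placebo, whose nature the protocol does not describe, an unmasked preparer and an unblinding procedure. It would also affect who applies the sintilimab-specific rules in 3.5. The objection is right that this costs far more than wording, and masked assessment does not require it.

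**Conclusion.** The point holds as a cheap improvement. The protocol fixes a single-blind design without stating who is blinded and provides no masked assessment of the progression call that decides both primary endpoints and ends treatment. The person making that call is probably, not certainly, unmasked. If so, differential calling could favour sintilimab despite the placebo and matched follow-up.

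Under the stated assumptions the size is modest for partial deferral (HR about 0.94 to 0.95 at one half). At the extreme bound of deferring every call it is material: HR about 0.87, with false positives a little over twice nominal. With about 31 events, a few calls carry weight.

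A reader might conclude that masked reading would remove the bias. It would only reduce it. Progression declared on clinical grounds, the timing of scans, and unmasking through immune-related events would remain. The imaging listed in 3.4.3 is of chest and abdomen, so recurrence in the head and neck may be judged outside those reads.

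**What to change.** In 3.3, state who is blinded. In 3.3 and 3.4.3, state that the radiologists who already read the trial CTs, and the existing team member who assigns RECIST response and the progression date, do so without knowledge of the arm. Support this with imaging requests that omit the arm and an allocation list kept from these people.

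No additional reader, visit or patient procedure is needed, and treating staff need not be blinded. The cost is protocol wording and the small continuing work of keeping the allocation from the assessors.
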